**Treatment Groups and Duration:**

In Cohort 1, if no clinical effect is observed in the sentinel subject, the DRC will decide whether to proceed with the randomization of 4 additional subjects (3:1, JK07: placebo) to receive blinded IP. Once the last subject in Cohort 1 completes the evaluation period, the DRC will decide whether to proceed to Cohort 2. The evaluation period for dose escalation to the next cohort will be at a minimum, the available safety data through Day 15 following the administration of the IP on Day 1 for all subjects in the current dose cohort. Safety data will continue to be collected

up to 180 days following the administration of the IP and may additionally be taken into consideration for dose escalation when available. Cohort 2 and subsequent cohorts will proceed as Cohort 1 until either of the following occur: a sentinel subject exhibits, in the opinion of the DRC, a clinical effect (efficacy or safety observation), or a cohort exhibits, in the opinion of the DRC, a clinical effect.

Once a clinical effect is observed, the DRC may, at its discretion, expand the size of that cohort in which a clinical effect is first observed, and subsequent cohorts, up to a maximum of 9 subjects (1 open-label JK07 sentinel subject, and 6:2 [JK07: placebo] randomized, double-blind subjects).

Following observation of a clinical effect and a decision to expand the size of the cohort at which the clinical effect was observed, the DRC will decide whether to dose escalate after the last subject in the expansion cohort completes the evaluation period. If the DRC decides to escalate the dose, a single unblinded sentinel subject will receive JK07 at the next dose level. If following the completion of the evaluation period of that sentinel subject the DRC decides to proceed, the remainder of the subjects in the expanded cohort size will receive JK07 or placebo according to the direction of the DRC, and this sequence will repeat until the highest planned dose level is reached or until the DRC determines not to dose escalate further.

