The study will also include a sentinel subject (1 active treated subject) in each dosing cohort to protect the population involved in the study by potentially identifying any serious AE in a single subject prior to exposing an entire cohort to the treatment, thereby increasing the level of safety in this JK07 phase 1 trial. The low(er) dose cohorts are sized at 5 subjects (1 active lead-in followed by a randomized active: placebo [3:1] main cohort) to effectively escalate through dose levels not anticipated to exert any effects. Dose escalation will not occur until at least 14 days of safety data (i.e., through Day 15) have been evaluated by the DRC and the dose has been established as safe and well tolerated. Following observation of a clinical effect, the DRC has the option to expand the size of the cohort at which the clinical effect was observed and subsequent cohorts to a total of 9 subjects (1 active lead-in followed by a randomized active: placebo [6:2] main cohort). The expanded cohort size will allow a more robust evaluation of JK07 doses with clinical activity. All cohorts shall proceed per the treatment algorithm, with continuous monitoring of emerging safety data, including clinical signs, laboratory values, and cardiac safety monitoring. Although it is appreciated that some adverse effects could take longer to manifest, it is believed that the time frame between the dosing of the sentinel subject and the subsequent cohort of approximately 5x the anticipated half-life ( $t_{1/2}$ ) of the JK07 is enough to minimize this risk.

A GLP-compliant 4-week repeated-dose toxicity study in cynomolgus monkeys showed minimal and transient JK07-related prolongation in QTca intervals (the maximum increase recorded was approximately 23 msec; a QTca dose response was not evident). The current phase 1 study requires subjects to be confined in the hospital on continuous 12-lead Holter/telemetry combination prior to dose administration and for

48 hours following dose administration. Baseline-corrected (clock-time matched) QT and QT interval corrected for heart rate using Fridericia's correction formula (QTcF) intervals will be evaluated for potential effects by JK07. If effects are evident, a concentration-response relationship between time-matched JK07 concentrations and change in QTcF interval will be explored.

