### 9.2 Sample Size Determination

The study will enroll up to a maximum of 63 subjects who will be randomized into dose escalation cohorts. The sample size is not based on statistical considerations but is typical for studies of this nature and is considered adequate to characterize the distribution of the planned endpoints. Any statistical testing will be considered exploratory and descriptive.

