		Additional biomarkers	CPK b , CPK-MB b , Troponin I c and/or hs Troponin T c , hsCRP c , LDH
90		Chemistry a	
		Hematology	
		Additional biomarkers	CPK b , CPK-MB b , Troponin I c and/or hs Troponin T c , hsCRP, LDH
135		Chemistry a	
		Hematology	
		Additional biomarkers	CPK b , CPK-MB b , Troponin I c and/or hs Troponin T c , hsCRP c , LDH
180		Chemistry a	
		Hematology	
		Additional biomarkers	CPK b , CPK-MB b , Troponin I c and/or hs Troponin T c , hsCRP c , LDH
End-of-study (prior to Day 180 due to patient or investigator- initiated withdrawal)		Chemistry a	
		Hematology	
		Coagulation	
		Additional biomarkers	CPK b , CPK-MB b , Troponin I c and/or hs Troponin T c , hsCRP

Abbreviations: β-hCG, beta human chorionic gonadotrophin; CPK, creatine phosphokinase; CPK-MB, creatine phosphokinase – muscle brain fraction; hs-CRP, high sensitivity C-reactive protein; LDH, lactate dehydrogenase

a All clinical chemistries are to be drawn FASTING >10hours.

b For safety laboratory assessments performed by the local laboratory, if CPK and CPK-MB are not included together on a single panel, then CPK-MB alone can be measured. If CPK and CPK-MB are not included together on a single panel and there is no local test available for CPK-MB, then the test may be omitted.

c For local laboratory safety assessments, only one of either Troponin I or hs Troponin T must be included, and the second biomarker may be optionally included.

Investigators must document their review of each laboratory safety report.

Laboratory results that could unblind any blinded cohort will not be reported to study centers or other blinded personnel until the cohort has been unblinded.

**Table 15 Schedule of Protocol-required Blood Collections to be Obtained by the Local Laboratory for Central Laboratory Analysis**

Day	Sample to be Collected for Central Lab Analysis by the Local Laboratory
Day 1 (Pre-infusion)	Exploratory biomarkers a / PK / Immunogenicity
Day 1 (End of infusion [EoI])	PK
Day 1 (0.5 hour from EoI)	PK
Day 1 (1 hour from EoI)	PK
Day 1 (2 hours from EoI)	PK
Day 1 (4 hours from EoI)	PK
Day 1 (8 hours from EoI)	PK
Day 1 (12 hours from EoI)	PK

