### **C. Sample Size**

Approximately 8 investigators and study centers are expected to participate in this study. A maximum of 63 subjects will be enrolled in the dose escalation cohorts. Five dose cohorts are planned. Two additional cohorts may be added as per the Data Review Committee (DRC) recommendation (total up to 7 cohorts) to receive IP.

For this study, no prospective calculations of statistical power have been made. The sample size is not based on statistical considerations but is typical for studies of this nature and is considered adequate to characterize the distribution of the planned endpoints. Any statistical testing will be considered exploratory and descriptive.

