## **E. Multiple Study Centers**

No adjustment for study center is planned. Data from all investigational sites will be pooled in the analyses.

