## **X. Exploratory Biomarkers**

The analyses described in this section will be performed at CR Medicon.

The analysis of exploratory biomarkers will be performed using the exploratory PD/biomarker evaluation population. Descriptive summary statistics will be reported for the actual observed and change from baseline for the following biomarkers (hsCRP, troponin-I or hs-troponin T, CPK, CPK-MB, lactate dehydrogenase, NT-proBNP and total BNP) by treatment groups and visits (Day 1 pre-infusion, Day 2, 7, 15, 30, 60, 90, 135, 180 (or end of study visit)). Baseline values are those obtained at pre-infusion on Day 1.

Separate summaries will be produced for results collected by Local labs (in the EDC system) and by Central labs (by Q vendor).

Exploratory biomarker results will be listed.

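### SAP X pools local troponin, CPK, CPK-MB and LDH over about 8 sites on their raw scale, with no common scale and no count of abnormal values

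*SAP*

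**What the plan says.** SAP Section X covers hsCRP, troponin I or hs-troponin T, CPK, CPK-MB, LDH, NT-proBNP and total BNP, by treatment group and visit: "Descriptive summary statistics will be reported for the actual observed and change from baseline for the following biomarkers". SAP V.M and IX.A give n, mean, SD, median, minimum and maximum. Neither section names a ratio, a log scale or a multiple of ULN.

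Local and central results are kept apart: "Separate summaries will be produced for results collected by Local labs" and, likewise, by the central laboratory. Within the local summary, sites are combined without adjustment (SAP V.E): "Data from all investigational sites will be pooled in the analyses". About 8 centers are expected.

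What a local laboratory measures may vary. Protocol Appendix 3, Table 14 says of troponin that "only one of either Troponin I or hs Troponin T must be included, and the second biomarker may be optionally included". Its footnote on CPK lets a site report CPK-MB alone when the two are not on one panel. Exclusion criterion 16 judges CPK and CK-MB in multiples of the institution's own ULN; SAP X does not carry that scaling over.

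Table 15 lists BNP, hsCRP, NT-proBNP, troponin I and hs-troponin T for central analysis. CPK, CPK-MB and LDH are not on that list.

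Protocol 9.4.3 promises a summary of the incidence of treatment-emergent abnormal laboratory values. SAP VII.C, which holds the shift tables, names hematology, chemistry, coagulation and urinalysis. In Protocol Table 13 the cardiac and muscle markers form a separate panel, additional biomarkers. The SAP's section on changes from the protocol explains only the omission for vital signs.

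**The concern.** Protocol 4.2 reports troponin I increases and myocardial degeneration in the monkey toxicity study, and gives these as the reason for monitoring this panel. The tables of these markers are therefore where a reader of the study report will look for myocardial injury.

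A raw mean over several laboratories weights each subject by the size of the numbers that the local assay produces. With 4 to 7 JK07 subjects per dose, one subject's rise may be large against that subject's own reference range and still move the group mean little. A count of subjects above ULN would not have this weakness, but none is planned for these markers.

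**Working it through.** **Group sizes.** The SAP has no power calculation to reproduce ("For this study, no prospective calculations of statistical power have been made"). The only sample-size figure is the maximum ("The study will enroll up to a maximum of 63 subjects who will be randomized into dose escalation cohorts"), and 7 cohorts × 9 = 63 reproduces it.
- Small cohort: "The low(er) dose cohorts are sized at 5 subjects (1 active lead-in followed by a randomized active: placebo [3:1] main cohort", so 1 + 3 = 4 on JK07 and 1 on placebo.
- Expanded cohort: "1 open-label JK07 sentinel subject, and 6:2 [JK07: placebo] randomized, double-blind subjects", so 1 + 6 = 7 on JK07 and 2 on placebo.
- Pooled placebo: from 5 × 1 = 5 to 7 × 2 = 14.

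**Spread over laboratories.** Assume one laboratory per site and subjects spread evenly over 8. The expected number of laboratories among n subjects is 8 × (1 − (7/8)^n), which is 3.3 for n = 4 and 4.9 for n = 7. A dose group will normally mix laboratories.

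**Masking.** The documents give no scale ratio, so k is an assumption shown over a range. Let m of n subjects be on an assay reading k times higher than the other, with every baseline equal on its own scale.
- The raw baseline mean is (mk + n − m)/n.
- A 5-fold rise in one smaller-scale subject adds 4/n.
- The relative lift of the raw mean is therefore 4/(mk + n − m).
- After division by the site's own ULN it is 4/n, whatever k is.

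| k | n = 4, m = 2: 4/(2k + 2) | n = 7, m = 3: 4/(3k + 4) |
|---|---|---|
| 1 | 100% | 57% |
| 1.2 | 91% | 53% |
| 2 | 67% | 40% |
| 5 | 33% | 21% |
| 10 | 18% | 12% |
| 100 | 2% | 1.3% |
| any k, scaled to ULN | 100% | 57% |

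The distortion runs both ways. If the injured subject is on the larger-scale assay, n = 4 and k = 10, the raw mean rises by 4 × 10/22 = 182%.

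**With random variation.** 100,000 simulated groups; assumed log SD 0.5 between and 0.2 within subjects; one smaller-scale subject with a 5-fold rise. The entries are the chance that the group's mean change exceeds the 95th percentile seen with no injury.

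| k | raw, n = 4 | raw, n = 7 |
|---|---|---|
| 1 | 96% | 91% |
| 2 | 86% | 77% |
| 5 | 49% | 40% |
| 10 | 23% | 18% |
| 100 | 6% | 6% |

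Scaled to ULN, the chance is about 96% (n = 4) and 90% (n = 7) at every k. For the mean log ratio to baseline it is about 88% and 69% at every k. The log ratio removes the scale but is less sensitive to one injured subject.

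**A shift in the whole group.** Now suppose every JK07 subject doubles, with an assumed log SD of 0.9 between and 0.3 within subjects. The entries are the chance that a 90% CI for the difference from placebo excludes zero.

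| Assay scales | 7 v 14, raw change | 7 v 14, log ratio | 4 v 5, raw change | 4 v 5, log ratio |
|---|---|---|---|---|
| one assay | about 70% | 95% | about 36% | 68% |
| 1:3:10 | 47% | 95% | 22% | 68% |

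At 7 v 14 the raw analysis loses about 25 points to skewness alone (95 − 70) and about 23 more to mixed scales (70 − 47). At 4 v 5 the losses are about 32 and 14. With scales of 1:1.2:1.5 the raw results (68% and 35%) are close to those for one assay. With no effect and scales 1:3:10, raw change at 7 v 14 excludes zero about 7% of the time against a nominal 10%.

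**The case against.** The strongest reply is that detection of injury does not rest on a local group mean. Central troponin I and hs-troponin T are drawn at every visit that SAP X lists and are summarized separately. The maximum is tabulated. SAP IX.A flags out-of-range values in the listings where applicable. Protocol 8.2.7 and 8.3.7 require investigators to review results and record clinically significant ones as adverse events, and Protocol 4.6 makes signs of ischemia or infarction possible dose-limiting events. All of this stands, so the gap concerns the summary tables and not safety oversight. It does not reach CPK, CPK-MB or LDH centrally, although Protocol 8.8 sends serum biomarker samples to the sponsor's designated laboratory without saying which analytes are run there. The local samples at 4, 8 and 12 hours and on Day 3 also fall outside the visits SAP X lists.

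The documents do not say that assays differ within one analyte, or that troponin I and T share a row; the table shells are a separate document. Both remain assumptions. SAP VII.C does refer to shift tables for all laboratory tests, but its own list of panels omits this one.

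The analysis is descriptive, and placebo comparisons are optional. The CI exclusion rates are therefore a yardstick for comparing summaries, not a planned test.

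Three stronger readings are tempting and are not supported:
- **The local mean mostly reflects one assay.** With share p of subjects on the larger-scale assay, that assay carries pk/(pk + 1 − p) of the mean. This exceeds half only if k > (1 − p)/p, for example k > 3 when p is one quarter.
- **Changes differ between dose groups simply because sites differ.** A scale factor applied to no change gives no change on average, and the no-effect simulation shows no excess of false differences. The statement could apply only to observed values.
- **The raw mean hides myocardial injury.** The central results, maximum, listings and adverse event review above rule this out as a statement about the whole plan.

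**Conclusion.** The concern holds as a cheap improvement. SAP X gives no rule for putting local troponin, CPK, CPK-MB and LDH on a common scale before sites are pooled. No planned table clearly delivers, for this panel, the incidence of abnormal values that Protocol 9.4.3 promises.

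The size depends on an unknown scale ratio. Masking is small at 1.2-fold (a lift of 91% instead of 100% with 4 subjects) and substantial from about 5-fold (33% instead of 100%). These figures assume two scales, a near-even split of subjects and a 5-fold rise in one of them. The gap matters most for CPK, CPK-MB and LDH, which have no central result in Table 15.

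Skewness is a separate reason to add a ratio to baseline, and it also applies to the central markers. Under the assumed SDs it accounts for about half of the loss at 7 v 14 and more at 4 v 5.

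**What to change.** In SAP X, for local results:
- give troponin I and hs-troponin T separate rows;
- summarize each marker as multiples of the site's own ULN;
- report the number and percentage of subjects above ULN, and newly above ULN, by treatment and visit.

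Name the central result as the main one for troponin and hsCRP.

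For these skewed markers, including central NT-proBNP and BNP, add the geometric mean ratio to Day 1 pre-infusion with a 90% CI. Keep the raw summary and the maximum beside it, because the log ratio is less sensitive to a single injured subject.

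The cost is SAP wording and table programming. Local reference ranges must be held in the database; the flagging rule in SAP IX.A already presumes that reference ranges are available.

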t Subjects who do not complete all required visits or withdraw from the study early are required to complete End-of Study/Early-Termination assessments (Day 180) as described in [Section 7.2](#).

u Randomization will occur approximately one to two weeks prior to scheduled date of IP infusion, at the time of scheduling the inpatient admission, and will trigger shipment of IP and administration kit to site. See [Section 6.3](#) for description of randomization procedures.

v Study visits on Day 11 and Day 22 may be conducted remotely at the discretion of the Principal Investigator based on their local risk assessment, in which case, the requirement for vital signs, ECGs, physical examination, and PK blood draws will be waived. The procedures will be performed as per the SoA if the visit takes place at the clinical site.

NOTE: See [Appendix 3 Clinical Laboratory Tests](#), [Table 13](#) for a complete list of protocol-required laboratory assessments that will be performed; see [Table 14](#) for a list of safety laboratory assessments (and assessment timepoints) that will be performed by the local laboratory; see [Table 15](#) for a list of safety and exploratory biomarker assessments that will be performed by a central laboratory.

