### **7.2 Subject Discontinuation/Withdrawal from the Study**

A subject may withdraw from the study at any time at his/her own request or may be withdrawn at any time at the discretion of the Investigator for safety, behavioral, compliance, or administrative reasons.

The following actions must be taken if a subject discontinues or withdraws from the study:

- If the subject withdraws consent for disclosure of future information, the Sponsor may retain and continue to use any data collected before such a withdrawal of consent.
- If a subject withdraws from the study, he/she may request destruction of any samples taken and not tested, and the Investigator must document this in the study center study records.
- See Table 1 SoA, End of Study visit (Day 180) for data to be collected at the time of study discontinuation. Should a subject request or decide to withdraw from the study prior to the End of Study visit, all efforts must be made to complete and report the observations as thoroughly as possible up to the date of withdrawal. Subjects withdrawing due to an AE at any time should be followed up until resolution, stabilization, the event is otherwise explained, the subject is lost to follow-up ([Section 8.3.8](#)) or until the end of their participation in the study. Subjects should be encouraged to complete the End of Study visit activities.
- Subjects who voluntarily withdraw will be termed dropouts. Dropouts and subjects withdrawn due to protocol violations may be replaced following discussion with the Principal Investigator and Sponsor.

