Day 2 (24 hours from EoI)	Exploratory biomarkers a / PK
Day 3 (48 hours from EoI)	PK
Day 4 (72 hours from EoI)	PK / Immunogenicity
Day 7	Exploratory biomarkers a / PK / Immunogenicity
Day 11	PK
Day 15	Exploratory biomarkers a / PK / Immunogenicity
Day 22	PK
Day 30	Exploratory biomarkers a / PK / Immunogenicity
Day 60	Exploratory biomarkers a / PK
Day 90	Exploratory biomarkers a / Immunogenicity
Day 135	Exploratory biomarkers a
Day 180 / End of Study Visit	Exploratory biomarkers a / Immunogenicity

Abbreviations: EOI, end of infusion; PK, pharmacokinetics

a BNP, hsCRP, NT-proBNP, Troponin I, hs Troponin T

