## **XI. Immunogenicity Assessments**

The analyses described in this section will be performed at CR Medicon.

Subjects who received placebo will be combined into 1 treatment group for purposes of analysis.

Serum samples for the antibody assays will be collected at Day 1, 4, 7, 15, 30, 90 and EOS/180. Additionally, subjects who do not complete all required visits or withdraw from the study early are required to complete End-of Study/Early-Termination assessments. The serum samples for antibodies will be assayed for neutralizing antibodies.

Immunogenicity will be evaluated using descriptive statistics. The number and percentage of subjects for ADA and neutralizing antibodies results will be summarized by treatment at scheduled time point as well as all post-baseline visits. Percentages for the neutralizing antibody result are based on the number of positive ADA results at that visit. ADAnalysisA titers of subjects who becomes antibody positive will be summarized by treatment and cohort as received along with nominal collection time. Summary statistics including n, min, max, mean and median will be calculated. In addition, incidence of early and delayed-type hypersensitivity responses will be summarized by ADA results (positive or negative) and by treatment.

Antibody information of subjects will be presented in the form of data listings.

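### The Day 180 biomarker row accepts an end-of-study visit on any study day, so early-termination values can be reported as Day 180; echo and antibody summaries probably share the gap

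*SAP*

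**What the plan says.** **Biomarkers, analysis.** SAP X summarizes observed values and changes from baseline by treatment group and visit. After the pre-infusion sample, the visits are "Day 2, 7, 15, 30, 60, 90, 135, 180 (or end of study visit". Day 180 and the end-of-study visit share one entry. The same list serves the separate local-laboratory and central-laboratory summaries.

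**Collection at withdrawal.** Footnote t to the EOS/180 column of protocol Table 1 reads: "Subjects who do not complete all required visits or withdraw from the study early are required to complete End-of Study/Early-Termination assessments (Day 180". Section 7.2 gives the timing: "See Table 1 SoA, End of Study visit (Day 180) for data to be collected at the time of study discontinuation". Table 15, the central-laboratory schedule, has one row, "Day 180 / End of Study Visit", for exploratory biomarkers and immunogenicity. Table 14, the local-laboratory schedule, has a Day 180 row and a separate end-of-study row marked "prior to Day 180 due to patient or investigator- initiated withdrawal".

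**Antibodies.** SAP XI says: "Serum samples for the antibody assays will be collected at Day 1, 4, 7, 15, 30, 90 and EOS/180". Its next sentence requires early-termination assessments from subjects who withdraw. Results are then summarized at scheduled time points and across all post-baseline visits.

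**Echo.** SAP IX.A summarizes 2D-TTE at scheduled time points and refers to the protocol's Schedule of Activities.

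**Windows.** Table 1 allows +/-10 days for the Day 180 visit. SAP V.C defines study day, but no SAP section uses it to assign assessments to visits.

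**The concern.** The Day 180 row is the last look at whether an effect of a single dose persists. If a subject leaves in the first weeks, has termination assessments, and those values are tabulated under Day 180, the row mixes two different times after dosing. A value taken near peak effect would make the effect look more lasting than it is. A value taken during acute worsening would do the reverse. In the by-visit antibody table, a subject sampled before antibodies form could count as negative at Day 180.

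Reporting an early value under Day 180 also works like carrying it forward, which sits poorly with the rule in SAP V.D that missing data are not imputed. Early leavers are not otherwise filtered out. The PD/biomarker population in SAP V.K needs only one post-baseline endpoint, and protocol Section 9.4.5 keeps withdrawn subjects' data in the analyses of all outcomes.

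**Working it through.** The plan states no figure to reproduce here. The check is of the text first, then of scale.

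**Step 1: is the pooling in the text?**

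- *Biomarkers: yes.* SAP X offers Day 180 or the end-of-study visit as one entry with no limit on the day. Section 7.2 has the Day 180 assessments done when the subject discontinues, which can be any day. Table 15 gives the two one row.
- *Antibodies: by inference.* SAP XI names EOS/180 as the last time point, adds termination samples, and summarizes by scheduled time point. No sentence assigns the termination samples to Day 180.
- *Echo: by inference.* SAP IX.A points to the Schedule of Activities, where the only slot for a termination echo is the EOS/180 column with footnote t.

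**Step 2: weight of one early value.**

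Inputs: a cohort has 5 to 9 subjects (protocol Section 4.1): one JK07 sentinel plus 3:1, or one plus 6:2. That gives 1 + 3 = 4 or 1 + 6 = 7 on JK07, and 1 or 2 on placebo. Placebo is pooled across cohorts (SAP V.M).

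With k early values among n in the row, their share is k/n. The row mean shifts by (k/n) x D, where D is the average gap between the early values and those subjects' true Day 180 values. For k = 1 and a full row:

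| Row | n | Share | Shift |
|---|---|---|---|
| JK07, 5-subject cohort | 4 | 25.0% | 0.25 D |
| JK07, 9-subject cohort | 7 | 14.3% | 0.14 D |
| Pooled placebo, 5 cohorts x 1 | 5 | 20.0% | 0.20 D |
| Pooled placebo, 7 cohorts x 2 | 14 | 7.1% | 0.07 D |

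If other subjects have no Day 180 value, n falls and the share rises.

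Illustration with assumed values: the true LVEF change is +6 points at Day 20 and +2 at Day 180. One Day 20 leaver moves a four-subject Day 180 mean from 2.0 to (3 x 2 + 6)/4 = 3.0, and a seven-subject mean to (6 x 2 + 6)/7 = 2.6. That assessment is 180 - 20 = 160 days from its label, against a visit window of +/-10 days.

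**Step 3: how often could it happen?**

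The documents give no dropout rate. With an assumed early-termination risk p per subject, the chance of at least one in a row is 1 - (1 - p)^n:

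| p | n = 4 | n = 7 |
|---|---|---|
| 5% | 18.5% | 30.2% |
| 10% | 34.4% | 52.2% |
| 20% | 59.0% | 79.0% |

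These are upper figures for pooling, since the subject must also complete the termination assessments outside Days 170 to 190.

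**Step 4: would mapping by actual day be enough?**

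Days 9 to 169 are 161 days. The Table 1 windows for visits with biomarkers in that span are Day 15 (5 days), Day 30 (5), Day 60 (11), Day 90 (11) and Day 135 (15), in total 47 days. So 161 - 47 = 114 days, or 71%, lie in no biomarker window. Day 20 falls in the Day 22 window, where no biomarker, echo or antibody sample is scheduled. Mapping alone would leave most termination values unplaced, so a separate row or listing is needed.

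**The case against.** The strongest reply is that the end-of-study visit is simply another name for Day 180. Protocol Section 8.2 uses it that way, and Section 7.2 speaks of withdrawal before that visit. On this reading, the parenthesis in SAP X is a synonym. The ambiguity is real. But the parenthesis is worded as an alternative, footnote t sends early leavers to that visit, and Table 14 uses the term for a visit before Day 180. Even if it is a synonym, the SAP has no rule for displaying termination values.

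It can also be said that footnote t, Section 7.2 and Table 15 govern collection, not analysis. That stands for echo and antibodies, where the mapping is inferred.

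Four stronger readings are tempting, and the documents do not support them:

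- *Day 180 is the only late time point.* Table 1 schedules echo and biomarkers at Days 60, 90 and 135, and antibodies at Day 90.
- *The primary antibody endpoint is compromised.* That endpoint is the presence of antibodies, and SAP XI also summarizes all post-baseline visits. That summary does not depend on the visit label.
- *SAP X contradicts the protocol's laboratory schedule.* Table 14's separate row concerns local collection and carries a different panel: it includes coagulation, which the Day 180 row omits. SAP X matches the central-laboratory Table 15.
- *All by-visit safety summaries are affected.* The safety sections of the SAP contain no wording like that in SAP X.

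Finally, the summaries are descriptive, no dose-escalation rule uses a Day 180 mean, and SAP V.M orders listings by date and time of assessment. An off-schedule value could therefore be found. This limits the harm but does not correct the summary table.

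**Conclusion.** The point holds. As written, the SAP lets a biomarker value from any end-of-study visit enter the Day 180 row, and no windowing rule prevents it. For echo and antibodies the same outcome is likely, because EOS/180 is the only slot for a termination visit, but it is not stated.

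One such value is 14% to 25% of a full JK07 row. The resulting bias is that share times the gap between the early and true Day 180 values, and the documents do not give that gap. It arises only if a subject leaves early and has termination assessments, and the number who do so cannot be known from the plan. The consequence is a mislabelled late row in descriptive tables, which is worth correcting before database lock. It does not undermine the trial's antibody incidence or its other late visits.

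**What to change.** - In SAP X, replace the last entry of the visit list with: Day 180, actual study day 170 to 190. This is the protocol's own +/-10-day window.
- State the same limit for the EOS/180 time point in SAP IX.A and SAP XI.
- Show early-termination assessments outside that window in a separate early-termination row or in listings. Keep them in any summary over all post-baseline visits, such as the antibody summary in SAP XI.
- If termination values are instead mapped by actual study day, map them only to visits at which that assessment is scheduled. Give the scheduled value priority when both fall in one window.

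This needs SAP wording and one visit derivation. It needs no new data and no change in study conduct. The Day 180 n may be slightly smaller.
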